## 5 Study Drug

### 5.1 Description

**See section 1.2**

### 5.2 Treatment Regimen

**See section 1.4**

### 5.3 Method for Assigning Subjects to Treatment Groups

All subjects whose CD5+ B cells account for less than 43% of total CD19 B cells will be assigned to maintenance therapy. Those subjects with CD5+CD19+ B cells  $\geq 43\%$  will be randomized as follows:

Random block:	1	1	6	2
Subject 5 by strata	A	A	B	A
Subject 6 by strata	B	B	A	B
Subject 7 by strata	B	B	A	A
Subject 8 by strata	A	A	B	B

#### Maintenance Therapies

##### Rituxan

A prescription for the drug will be written by the nephrologist managing the subject's care and will be arranged with a UNC infusion center. The physician will discuss the drug with the subject and provide a printout of information about the drug. The drug will be administered as described below at a dose of 500mg.

### Preparation and Administration of Study Drug

The preparation of rituximab for infusion will be performed by the UNC hospitals pharmacy according to their standard operating procedures for clinical use.

- Step 1. Insert PIV
- Step 2. Flush line with sodium chloride 0.9% 10 mL
- Step 3. Administer premeds acetaminophen 650 mg orally and diphenhydramine 25 mg orally.
- Step 4. Infuse rituximab 500 mg in sodium chloride (NS) 0.9% 500 mL IVPB started at 50/mg/hour; rate increase done, and vitals monitored according to protocol for 1st dose (see doc flowsheet).
- Step 5. Flush line with sodium chloride 0.9% 10 mL
- Step 6. Remove PIV; apply pressure and wrap infusion site.
- Step 7. Ensure that patient is having no ill effects of the treatment and discharge from clinic.

### **HOW SUPPLIED/STORAGE AND HANDLING**

Rituxan vials [100 mg/10 mL single-use vials (NDC 50242-051-21) and 500 mg/50 mL single-use vials (NDC 50242-053-06)] are stable at 2°C–8°C (36°F–46°F). Rituxan vials should be protected from direct sunlight. Do not freeze or shake.

### Mycophenolate Mofetil

A prescription for the drug will be written by the nephrologist managing the subject's care and will be sent to the pharmacy of the subject's choice. The physician will discuss the drug with the subject and provide a printout of information about the drug. Patients are typically started at a dose of mycophenolate mofetil 500 mg ((or equivalent dose of mycophenolic acid) twice daily and the dose is titrated up to 750 mg twice daily after 2 weeks and again to 1000 mg twice daily 2 weeks later based on patients' tolerability. The drug will be taken orally and self-administered by the patient. The patient will take the drug on an empty stomach at least 1 hour before or 2 hours after a meal and will swallow it whole. The subject will be instructed to store the drug at room temperature (59° to 86°F) away from moisture and heat and to keep the bottle tightly closed.

### **HOW SUPPLIED**

250 mg capsule

Blue-brown, two-piece hard gelatin capsules, printed in black with "CellCept 250" on the blue cap and "Roche" on the brown body.

500 mg tablets

Lavender-colored, caplet-shaped, film-coated tablets printed in black with "CellCept 500" on one side and "Roche" on the other.

Mycophenolate mofetil is also available in generic formulation.

### Azathioprine

A prescription for the drug will be written by the nephrologist managing the subject's care and will be sent to the pharmacy of the subject's choice. The physician will discuss the drug with the subject and provide a printout of information about the drug. The subject will be instructed to take a dose equivalent to 1.5-2 mg/kg once a day. The drug will be taken orally and self-administered by the patient. The patient will take the drug with food. The subject will be instructed to store the drug at room temperature (59° to 86°F) away from moisture and heat and to keep the bottle tightly closed.

### **HOW SUPPLIED:**

50 mg overlapping circle-shaped, yellow to off-white, scored tablets imprinted with "IMURAN" and "50" on each tablet. Azathioprine is also available in generic formulation.

## **5.4 Subject Compliance Monitoring**

For patients assigned to receive maintenance therapy:

We will schedule infusion clinic visits for patients who will receive rituximab therapy and we will reschedule any missed infusion visits to ensure that they receive treatment.

We will ask patients taking mycophenolate mofetil or azathioprine questions about medication adherence at each visit and emphasize the importance of taking their medication as prescribed.

## **5.5 Prior and Concomitant Therapy**

At the time of enrollment, all patient will have received induction therapy with corticosteroids in combination with cyclophosphamide or rituximab as described above. The choice of therapy (rituximab or cyclophosphamide), doses and number for doses and dates of infusions will be recorded. The number doses and number of doses of pulse methylprednisolone at the beginning of induction, as well as the doses and tapering schedule of daily oral prednisone will likewise be recorded.

For patients enrolled after induction treatment for relapsing vasculitis, the history of prior immunosuppressive therapy doses and dates will be extracted from the medical history or patient's record as available.

We will record all medications that subjects are currently taking at each visit from enrollment to the final follow up visit. We will record the name of each drug, dosage, frequency, start date, end date, and indication.

### **Which concomitant medicines/therapies (including rescue therapies) are permitted during the study**

Use and choice of prophylactic antibiotics will be left to the treating physician's decision, with no identified restrictions.

### **Which concomitant medicines/therapies are not permitted during the study (if applicable)**

Then use of maintenance oral cyclophosphamide, or the concomitant use of more than 1 maintenance immunosuppressant will not be allowed (e.g. rituximab + mycophenolate mofetil, or rituximab + azathioprine) will not be allowed. **Maintenance dose of prednisone cannot exceed 5 mg daily.** Patients requiring increased dose of prednisone, or combination immunosuppressant drugs will be deemed in relapse and to have reached the study endpoint. They will be withdrawn from the treatment protocol and followed for data collection only.

**Note about live vaccines:** Patients who are candidates for enrollment in the study will all have already received immunosuppressive therapy, and should not have received any live vaccine since the start of their immunosuppressive therapy. Should a patient have received a live vaccine in the 4 weeks prior to, or after enrollment, any maintenance immunosuppression for the prophylaxis against relapse (i.e., while the patient is clinically in remission) will be delayed for 4 weeks after the administration of the vaccine.

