### **3.2 Primary Study Endpoints**

Primary outcome measure is time to first relapse - defined as recurrence of any signs or symptoms attributable to active vasculitis consisting of at least 2 minor or 1 major item on the BVAS score (BVAS  $\geq 2$ ) - after a period of complete remission.

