### 7.2 Statistical Methods

As a proof-of-concept trial, no statistical comparisons will be done, but summary statistics and graphical displays of the data will be observed for patterns and also used to calculate sample size estimates needed for statistical comparisons in a larger trial. Summary statistical estimates of population parameters will be tabulated along with corresponding confidence intervals (CIs).

For the descriptions of each analytic Aim below groups, will be defined as follows:

Cohort 1: Subjects in remission with CD19+CD5+  $\geq 43\%$

- A) To discontinue maintenance immunosuppression (NO-Maintenance Therapy Group)
- B) To continue on maintenance immunosuppression (Maintenance Therapy Group)

Cohort 2: Subjects in remission with CD19+CD5+  $< 43\%$

- B) To continue on maintenance immunosuppression (Maintenance Therapy Group)

Aim 1. Characterize and compare A and B in terms of the outcome variables, based on data from Cohort 1.

Aim 2. Characterize and compare A and B in terms of the outcome variables, based on Cohorts 1 and 2 combined.

Aim 3. Characterize and compare Cohort 1(B) and Cohort 2(B).

Aim 4. Characterize and compare Cohort 1(A) and Cohort 2(B).

Aim 5. Obtain point- and interval-estimates needed to plan a future confirmatory randomized clinical trial.

Time to first relapse – we will summarize the time (months) to relapse and plot Kaplan-Meier curves for time to FIRST relapse by each regimen and cohort, and calculate median time to relapse and a 24-month relapse-free survival rate for each group. We will calculate a univariate hazard ratio with 95% confidence interval using Cox regression models. No statistical analyses for comparisons will be done, but trends and relapse estimates by regimen and by cohort will be used for formulating a larger study. We are most interested in time to first relapse as that denotes a clinical end point for the study since it will require reinitiating induction therapy rather than maintenance or “no maintenance”. However, we will continue to collect data on subjects with relapses for their full follow-up time to have some information on how these subjects respond to treatment and/or if they relapse again after being in this study.

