**Note about determination of relapse:** In cases where the assessment of relapse performed by [name] differs from that of the treating physician's assessment, the assessment used for final data analysis will be [name].

Missing Data: Missing values will not be imputed. For those who drop out of the study prior to reaching an outcome, they will contribute the time they were followed. For those who miss visits and do not have laboratory values assessed, we will use the next available to determine their time to normalization of a value. If patients report infections, we may not have details on the location or type, but will report the counts with and without patient-only reported infections (verification of infections by outside providers or hospitals will be included in the study counts and not be deemed as reported by the patient only). We anticipate minimal missing data as nearly all measures will be obtained in the setting of routine clinical practice. If patients are seen elsewhere, we will need to get outside medical records. Reasons for missing data and protocol violations will be documented in the database.

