#### **8.4 Stopping Rules**

Trial Termination: It is anticipated that some of the patients will have a relapse even among those treated with maintenance immunosuppression. In a recent large randomized controlled trial of maintenance therapy with rituximab vs azathioprine, 5% of patients in the rituximab-treated group and 29% of those in the azathioprine-treated group had a major relapse over 28 months of follow up (Guillevin L et al *N Engl J Med* 2014;371:1771-80.). Major relapses were defined as involving a major organ or life threatening (e.g. alveolar hemorrhage, glomerulonephritis, mononeuritis with new motor deficits). In addition, minor relapses (e.g. recurrence of epistaxis, arthralgias, or skin rash) occurred with greater frequency (e.g. in the RCT trial of maintenance therapy with rituximab vs azathioprine, minor relapses occurred in 11% vs 16% of patients respectively).

In order to minimize bias in the assessment of the primary endpoint of relapse, this relapse assessment will be done by a physician serving as a reviewer blinded to the patients' identity and treatment arm. [name], Associate Professor of Medicine, Associate Division Chief, Division of Rheumatology, Allergy, and Immunology at UNC will serve as the blinded reviewer for this study. [name] has vast experience and expertise in ANCA vasculitis. [name] will NOT be involved in the care of patients enrolled in this study. Every 3 months, [name] will review all of the available clinical assessments for relapse adjudications based on the BVAS scores, clinical history, review of systems, physical examination and laboratory data. A report form will be generated to provide him with this information while being blinded to the treatment arm (medication list will be omitted). Patients will be treated according to the treating-physician's assessment in the interval between these blinded reviews. [name] assessment will not be used to guide therapy. For the purpose of data analysis, in cases where the assessment of relapse done by [name] differs from the treating physician's assessment, the assessment used for final data analysis will be the blinded reviewer ([name]).

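### Section 5.5 declares the study endpoint reached on a treatment change alone, which contradicts the BVAS definition of relapse and is not expressly made subject to blinded adjudication

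*Combined protocol and SAP*

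**What the plan says.** Four places in the combined protocol and SAP bear on what counts as a first relapse.

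- **Section 5.5, therapies not permitted.** After barring more than one maintenance immunosuppressant and capping maintenance prednisone at 5 mg daily, it states: "Patients requiring increased dose of prednisone, or combination immunosuppressant drugs will be deemed in relapse and to have reached the study endpoint". It continues: "They will be withdrawn from the treatment protocol and followed for data collection only".
- **Sections 2 and 3.2.** The primary outcome is time to first relapse, meaning signs or symptoms attributable to active vasculitis, "consisting of at least 2 minor or 1 major item on the BVAS score", after complete remission. Treatment change is not part of the definition.
- **Section 7.2, note on determining relapse, and section 8.4.** Where the blinded reviewer and the treating physician differ, "the assessment used for final data analysis will be the blinded reviewer". Section 8.4 lists the reviewer's inputs as BVAS scores, history, review of systems, examination and laboratory data, and leaves the medication list off the report form.
- **Section 7.2, time to first relapse.** The outputs are Kaplan-Meier curves, a median, a 24-month relapse-free rate per group and a univariate Cox hazard ratio with its confidence interval. No statistical comparisons are planned. The summaries are to be "used to calculate sample size estimates needed for statistical comparisons in a larger trial".

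**The concern.** The plan has two routes to the same endpoint. One is clinical: BVAS items attributed to vasculitis, with a blinded reviewer prevailing in a disagreement. The other is a deeming rule triggered by a prescribing decision. They can classify the same patient differently, and no sentence says which one fixes the analysed event.

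The trial is open label, and under 8.4 patients are treated on the treating physician's assessment between three-monthly blinded reviews. If 5.5 were followed to the letter, a decision made with knowledge of the arm would become a primary event without passing through the adjudication that 8.4 sets up to limit bias. No error rate is at stake, because nothing is tested. What is at stake is the meaning of the relapse rates and hazard ratio that Aim 5 carries into the planning of a larger trial.

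**Working it through.** **Step 1. Set the rules side by side.**

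| Question | 5.5 | 2 and 3.2 | 7.2 note and 8.4 |
|---|---|---|---|
| Trigger | More prednisone, or combination drugs | Signs or symptoms with BVAS items | Reviewer's reading of the clinical data |
| BVAS threshold | None stated | 2 minor or 1 major | BVAS among the inputs |
| Attribution to vasculitis | None stated | Required | A matter for the reviewer |
| Adjudication | None stated | Not mentioned | Reviewer prevails if the two assessments differ |

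**Step 2. Test whether 7.2 and 8.4 already settle it.**

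- Case A: the physician escalates because of suspected vasculitis and judges the patient in relapse; the reviewer finds no qualifying BVAS items. The assessments differ, so the reviewer prevails. Section 5.5 still says that the endpoint has been reached, but 7.2 and 8.4 give a workable answer.
- Case B: the physician raises prednisone above 5 mg daily without judging it a relapse, and the reviewer also finds none. There is no disagreement, so the precedence rule is not triggered. Section 5.5, read literally, still declares the endpoint reached. Nothing says whether this patient is an event, is censored or stays at risk.

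Case B depends on reading 5.5 as covering an increase made for a reason other than vasculitis. The text does not exclude this, but does not clearly intend it either.

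**Step 3. Reproduce the plan's own numbers.** Section 7.1: 40 × 0.78 = 31.2, stated as about 31 randomised; 40 × 0.22 = 8.8, stated as 9 in the low-CD5+ group. Both agree. Then 31 / 2 = 15.5, so 15 to 16 per randomised arm; section 8.4 says about 15.

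**Step 4. Effect of one disputed patient on an arm's crude rate.** 1/16 = 6.3 points; 1/15 = 6.7 points. As an assumed example, moving from 2/15 to 3/15 moves the rate from 13.3% (exact 95% CI 1.7% to 40.5%) to 20.0% (4.3% to 48.1%).

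**Step 5. Illustration for the hazard ratio.** The documents give no expected event counts for this trial. Assume 15 per arm with full follow-up, constant hazards, 6 no-maintenance (WATCH) and 3 maintenance events when 5.5 counts, and no later adjudicated relapse in a reclassified patient. With H(x) = −ln(1 − x/15):

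- H(6) = 0.5108, H(5) = 0.4055, H(3) = 0.2231, H(2) = 0.1431.
- Counting 5.5: 0.5108 / 0.2231 = 2.29.
- Reviewer only, one WATCH patient reclassified: 0.4055 / 0.2231 = 1.82.
- Reviewer only, one maintenance patient reclassified: 0.5108 / 0.1431 = 3.57.
- Reviewer only, one in each arm: 0.4055 / 0.1431 = 2.83.

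The ratio can move either way.

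**Step 6. Compare with sampling error.** Approximate 95% CI at 6 versus 3 events: 2.29 × exp(±1.96 × √(1/6 + 1/3)) = 0.57 to 9.15. The exact 95% CI for 6/15 is 16.3% to 67.7%. Both are much wider than the shift from one patient.

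**The case against.** The best reply is that the plan already separates leaving treatment from the analysed event. Section 5.5 is a concomitant-therapy rule whose practical effect is withdrawal from protocol treatment with continued data collection. Section 8.4 says that relapse ends the interventional phase and that the reviewer's verdict does not guide therapy. The statistical section carries its own note on determining relapse. A physician who escalates for vasculitis has in effect judged the patient in relapse, so the reviewer's precedence applies. Most of this stands: reviewer precedence is the more natural reading. It does not remove the sentence in 5.5, which names the study endpoint and refers to no adjudication.

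Some stronger readings are tempting, and the documents do not support them.

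- **That 5.5 catches any prednisone increase.** The sentence follows directly on the 5 mg daily ceiling, so an increase above that ceiling is the likelier meaning.
- **That 7.2 also defines relapse by treatment**, because it says of first relapse "that denotes a clinical end point for the study since it will require reinitiating induction therapy". That describes what follows from a relapse and why it matters clinically. It does not make treatment a criterion.
- **That 3.2 itself gives the reviewer the decision.** It supplies the BVAS definition only; the reviewer appears in 7.2 and 8.4.
- **That the reviewer cannot know of an escalation.** The medication list is omitted as a blinding measure, but the clinical history is supplied and may reveal it.
- **That the estimate is biased in a known direction.** Disputed patients can arise in either arm, and the plan gives no basis for a net direction.
- **That WATCH patients restarted on a single agent without an adjudicated relapse leave a material gap.** They fall outside 5.5 and implicitly stay at risk. Assume 15 patients, one of them so treated in month 1 to 18, and 2, 5 or 8 evenly spaced relapses among the others. Keeping that patient at risk rather than censoring at treatment changes the 24-month Kaplan-Meier estimate by only 0 to 3.8 points.

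**Conclusion.** The point holds as a contradiction in the text, and it is minor. Section 5.5 states an endpoint rule that does not match the primary definition in sections 2 and 3.2, and the precedence rule in 7.2 and 8.4 only implies that adjudication governs it. Literal use of 5.5 would let open-label prescribing create primary events.

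The size is 6.3 to 6.7 points on an arm's crude 24-month rate for each patient who meets 5.5 and never has an adjudicated relapse, given 15 to 16 per arm. The number of such patients could be zero. The hazard ratio figures rest on assumed counts and serve only to show that one patient matters and that the direction is open. Sampling error is larger than any of these shifts. It is, however, reported through the confidence intervals, whereas an unsettled event definition is not. It would not be right to conclude that the trial's estimates are invalid or that the blinded adjudication has been abandoned.

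**What to change.** 1. **Section 5.5.** Replace the deeming sentence. Meeting the criterion (specify prednisone above 5 mg daily, or combination immunosuppression) ends the interventional phase, follow-up continues to 24 months, and the case goes to blinded review.
2. **Section 7.2.** State that only a reviewer-adjudicated relapse meeting the 3.2 definition counts as the primary event, whether or not the treating physician agrees and whether or not 5.5 was met.
3. **Optional.** List by arm the number of patients who met 5.5, or started immunosuppression for suspected vasculitis, without an adjudicated relapse. Section 5.5 already has drug, dose, dates and indication recorded at each visit.

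The cost is a sentence or two in each section and, if wanted, one line in a table. No new data or visits are needed. A separate time-to-event curve for treatment changes is not required; it would rest partly on the open-label decisions that adjudication is meant to keep out of the endpoint.

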## **5.6 Packaging**

The UNC pharmacy will mix IV bags for rituximab infusions.

Azathioprine and mycophenolate mofetil will be packaged in pill bottles used by commercial pharmacies to dispense drugs.

## **5.7 Receiving, Storage, Dispensing and Return**

The UNC Infusion Clinic will receive a pre-mixed rituximab IV bag from the UNC pharmacy on the day on which it will be administered. The bag will not be stored or returned.

Subjects taking MMF or azathioprine will receive the drug from the pharmacy of their choice. They will be instructed to store the drug at room temperature (59° to 86°F) away from moisture and heat and to keep the bottle tightly closed. Patients will be instructed to take leftover medication to their pharmacy for safe disposal.

### **5.7.1 Receipt of Drug Supplies**

N/A

### **5.7.2 Storage**

N/A

### **5.7.3 Dispensing of Study Drug**

The UNC Infusion Clinic will receive a pre-mixed rituximab IV bag from the UNC pharmacy on the day on which it will be administered. The bag will not be stored or returned.

Subjects taking MMF or azathioprine will receive the drug from the pharmacy of their choice.

## **6 Study Procedures**

**Pre-Screening:** Potential subjects will be identified by reviewing the medical records of patients being seen in the UNC Kidney and Hypertension Clinic.

**Enrollment Visit:** The research coordinator (RC) will identify patients who meet inclusion/exclusion criteria. If an identified patient's regular nephrologist is not a member of the study team, the RC will first contact that physician to obtain permission to approach the patient. The RC will meet with an identified/approved patient during a regularly scheduled clinic appointment in the UNC Kidney and Hypertension Clinic to discuss the study. The RC will provide an overview of the study to ascertain the patient's interest in participating. If interested, the RC will review the ICFs with the patient, providing ample time for the patient to review the forms and ask questions. If the patient has questions to ask a physician, a physician member of the study team will meet with the patient, discuss the study, and answer questions. If the patient decides to enroll in the study, s/he will be asked to sign the ICFs. The RC will make copies of the ICFs to give to the patient.

The patient will have a physical examination, which will include a Birmingham Vasculitis Activity Score (BVAS). If the patient has been seen within 2 weeks prior with a physical exam performed for SOC, this examination and the BVAS calculated at that visit may be used for enrollment data. The RC will collect information about demographics and concomitant medications from the subject. The subject will be asked to complete a quality of life (QOL) questionnaire. We will draw 24 ml of blood for research tests when the subject has blood drawn for routine labs. We will record the results of certain routine labs (creatinine, urinalysis, CBC, and ANCA tests), as well as results from the B cell tests in our study database.

After enrollment and obtention of CD5+ levels, subject will be assigned to receive maintenance therapy (low CD5+ B cell recovery <43%) or be randomized to either receive or not receive maintenance therapy (high CD5+ B cell recovery ≥43%).

